### 6.1.9. Derived Variables

Change from baseline = value at current time point – baseline value

$$\text{Percentage change from baseline} = \left( \frac{\text{value at current time point} - \text{baseline value}}{\text{baseline value}} \right) * 100\%$$

Treatment-emergent AE (TEAE) = any AE with an onset date/time on or after administration (including any partial administration) of the first dose of study intervention and through the study completion date from the end of study CRF. That is, if the start time for the AE is provided, then the AE start date and time will be compared with the first dose date and time in order to determine whether the AE is a TEAE. If the start time for the AE is not provided, then the AE start date will be compared with the first dose date. In this case if the AE start date is on or after the first dose date, then the AE is considered a TEAE.

#### Body Surface Area (BSA)

BSA will be calculated via the DuBois formula:

- $BSA (m^2) = 0.007184 \times \text{height(cm)}^{0.725} \times \text{weight(kg)}^{0.425}$

BSA Adjusted Uox: for participants aged <18 years, the 24-hour Uox values will be adjusted for BSA using the following formula prior to using the values in any analyses. The adjusted values will be used for all endpoint calculations. Participants aged  $\geq 18$  years will not have any adjustments performed to their 24-hour Uox results for the primary analysis. BSA Adjusted Uox values for all participants will be used for sensitivity analysis. All BSA Adjusted Uox values will use the BSA for the participant using the height and weight taken at same visit as the 24-hour Uox value.

- $BSA \text{ Adjusted Uox} = 24\text{-hour Uox value} * (1.73/BSA \text{ of participant})$

If the height and weight are not available from the same visit as the 24-hour Uox value, then the imputation rules described in section 6.1.10.3 Missing Height/Weight Measurements to be used for BSA Adjusted Uox Calculations will be used to impute the height and weight in order to calculate the BSA Adjusted Uox values.

## eGFR Equations

### Chronic Kidney Disease Epidemiology Collaboration (CKD-EPI) equation – for Adult Participants ( $\geq 18$ years)

- $eGFR = 141 \times \min(S_{Cr}/k, 1)^\alpha \times \max(S_{Cr}/k, 1)^{-1.209} \times 0.993^{Age} \times 1.018$  (if female)  $\times$  1.159 (if Black)

$S_{Cr}$  = standardized serum creatinine in mg/dL

$k = 0.7$  for females or  $0.9$  for males

$\alpha = -0.329$  for females or  $-0.411$  for males

min = minimum value

max = maximum value

age is in years

### Schwartz 2009 creatinine-based equation – for Pediatric Participants ( $< 18$ years of age)

- $eGFR = 36.5 \times \text{height}/SCr$

height is in centimeters

SCr = serum creatinine in  $\mu\text{mol/L}$

### Schwartz 2012 multivariate equation – for Pediatric Participants ( $< 18$ years of age)

- $eGFR = 39.8 \times [\text{ht}/\text{Scr}]^{0.456} \times [1.8/\text{cysC}]^{0.418} \times [30/\text{BUN}]^{0.079} \times 1.076^{\text{male}} \times [\text{ht}/1.4]^{0.179}$

ht = height in meters

Scr = serum creatinine in mg/dL

cysC = cystatin C in mg/L

BUN = blood urea nitrogen in mg/dL

[figure not shown]
male = 1 if the patient is a male; 0 otherwise

### Matsuo eGFR Equation - For Adult Participants in Japan

- $eGFR = 194 \times [\text{Cr}]^{-1.094} \times [\text{Age}]^{-0.287} (\times 0.739$  in females)

The above eGFR calculations will be performed by the central laboratory.

For adolescents who turn 18 during the course of the study, the equation used at baseline (eGFR 2009 Schwartz Creatinine-based equation) will be used throughout the study.

### Weight Adjusted 24-hour Urinary Creatinine Excretion (WTCREA24)

24-hour urinary creatinine excretion values (SDTM.LB CREAT24) will be merged with SDTM.VS records where VSTESTCD=WEIGHT and VSSTRESN is not missing.

[figure not shown]
$$\text{Calculate WTCREA24} = [\text{CREAT24}] / [\text{WEIGHT}]$$

### Area Under the Curve (AUC)

AUC24-hour Uox is calculated based on the percent change from baseline in Uox. The x-axis will be time in days and y-axis will be percent change from baseline in Uox. A percent decrease from baseline in Uox will be denoted as negative. A percent increase from baseline in Uox will be denoted as positive. The curve might be in its entirety, or at least in part, below the x-axis (Panel A, Figure 1). The area below the x-axis will be calculated and presented as a positive value. For an increase from baseline the percent change from baseline will be positive and that part of curve will be above the x-axis. The AUC would then be calculated as area below the axis minus area above the x-axis (Panel B, Figure 1). The AUC will be calculated using the trapezoidal rule; however, given that the percent change from baseline in Uox can change sign, we will use the approach outlined in the PharmaSUG by Jianfeng Ye.

The AUC will be calculated using the actual time in days between Uox collections, and not the nominal visit days. See Figure 1 for examples of the AUC, where the portion of the data to be used in calculation of the primary endpoint is contained within the orange box.

**Figure 1 Example of AUC Graphs for Primary Endpoint**

Panel A: All values below 0

Panel B: Values both above and below 0

AUC24-hour Uox: creatinine will be calculated as described above for Uox except that the AUC24-hour Uox: creatinine will be based on the percent change from baseline in the values of the Uox-to-creatinine ratio.

As illustrated in figure 1 above, the AUC for Day 90 to Day 180 is calculated based on the area underneath the 0 percent line between Day 90 and Day 180. For improvement in the subjects' condition, i.e. area below the zero percent line, we define the AUC as a positive number. For worsening of the subjects' condition, i.e. area above zero percent line, we define the AUC as a negative number. The final AUC will be the area below the zero percent line minus the area above zero percent line. The final AUC for each subject will be standardized based on 90 days.

- $AUC\_standardized = (AUC/actual\ days\ from\ Day90\ visit\ to\ Day180) \times 90$

If data are only partially available between day 90 and day 180 (i.e. assessment dates are missing at either day 90 or day 180), the standardization will assume the actual number of days elapsed to be 90.

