3. OBJECTIVES AND ENDPOINTS

Objectives	Endpoints
Primary	
To assess the efficacy of DCR-PHXC in reducing urinary oxalate burden in patients with PH	AUC from Day 90 to Day 180, based on percent change from Baseline in 24-hour Uox
Key Secondary	
To identify the proportion of participants with normalized or near-normalized Uox	The proportion of participants with a 24-hour Uox level < 0.46 mmol/24 hours or ≥ 0.46 to < 0.60 mmol/24 hours (adjusted per 1.73 m ² BSA in participants aged < 18 years) on at least 2 consecutive visits, beginning with Day 90
Secondary	
1. To evaluate the effect of DCR-PHXC on stone burden in patients with PH	1. Percent change in the summed surface area and number of kidney stones identified via kidney ultrasound from Baseline to Day 180
2. To evaluate the effect of DCR-PHXC on plasma oxalate in patients with PH	2. Percent change in plasma oxalate from Baseline to Day 180 (for adults only)
3. To evaluate the effect of DCR-PHXC on eGFR	3. Rate of change in eGFR from Baseline to Day 180
4. To assess the safety of DCR-PHXC in patients with PH	4. AE and SAE; change from Baseline in 12-lead ECG, physical examination findings, vital signs, and clinical laboratory tests
5. To characterize the PK of DCR-PHXC in patients with PH	5. Population and individual PK parameters for DCR-PHXC
Tertiary/Exploratory	
1. To evaluate the effect of DCR-PHXC on stone events in patients with PH	1. Number of stone events over a 6-month period
2. To assess the efficacy of DCR-PHXC in reducing Uox burden over 6 months in patients with PH	2. AUC of 24-hour Uox from Day 1 to Day 180, based on percent change from Baseline
3. To assess the efficacy of DCR-PHXC in reducing Uox at month 6 in patients with PH	3. Percent change in 24-hour Uox from Baseline to Day 180
4. To evaluate the effect of DCR-PHXC on urinary oxalate-to-creatinine ratio in patients with PH	4. AUC of 24-hour urinary oxalate-to-creatinine ratio from Day 90 to Day 180, based on percent change from Baseline
5. To evaluate the effect of DCR-PHXC on QoL Assessments in patients with PH	5. Change from Baseline to Day 180 in the SF-36 and EQ-5D-5L in adults; and in the PedsQL™ in children
6. To evaluate the relationship between Uox spot urine and 24-hour urine measurement in patients with PH	6. Uox in spot urine and 24-hour urine

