#### 3.2. Sample Size and Power

Approximately 40 participants will be screened to achieve an estimated total of 36 evaluable participants.

For the sample size calculations, the primary endpoint of  $AUC_{24\text{-hour } U_{ox}}$  from Day 90 to Day 180 based on percent change from baseline was used. The group sequential design with pre-specified alpha spending for interim analysis and final analysis was utilized. The randomization ratio is 2-to-1 (active-to-placebo). The primary hypothesis to be tested is a one-sided superiority hypothesis at the significance level of 0.025. The  $AUC_{24\text{-hour } U_{ox}}$  in the placebo arm is assumed to be 0, as the  $U_{ox}$  values may oscillate up and down from baseline due to measurement variability. The  $AUC_{24\text{-hour } U_{ox}}$  in the active arm is assumed to be 3600 based on a 40% decrease over the 90 days. The effect size is assumed to be 1.2. Under these assumptions, the sample size of 36 patients (24 in the active arm and 12 in the placebo arm) will yield a power of approximately 94%. All calculations were performed using [REDACTED].

The above sample size calculation was performed under the assumption that there may be an interim analysis to re-estimate sample size after two-thirds of participants complete the study. However due to late enrollment experienced in the study, an interim analysis will not be performed.

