## 8. Efficacy Analysis

All AUC parameters referenced in the efficacy analysis refer to the standardized AUCs defined in section 6.1.9.

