#### 8.4. Tertiary/Exploratory Efficacy Analysis

The same statistical model described above for the primary efficacy analysis will be applied to the following tertiary/exploratory efficacy endpoints.

- AUC24-hour Uox from Day 1 to Day 180, based on percent change from baseline (ITT population)
- Percent change in 24-hour Uox from baseline to Day 180 (ITT population)
- AUC24-hour Uox:creatinine from Day 90 to Day 180, based on percent change from baseline (MITT population)
- Change from baseline to Day 180 in the SF-36, EQ-5D-5L in adults, and in the PedsQLTM in children (ITT population)

The number of stone events over a 6-month period will be analyzed using an exact Poisson regression model. The model will include treatment group and baseline stone events rate (continuous). Baseline stone events rate will be the number of stone events observed over the past 12 months prior to dosing. The model will include an offset term for total follow-up time as the 'number of months exposed' equal to the total elapsed time between first dose date and last day of visit in the study, divided by 30.4375. Annualized stone event rate (number of stone events per year per person) will be derived as number of stone events in the exposure period / total number of years exposed.

Example SAS code is given below:

```
PROC GENMOD DATA=;  
  CLASS TREATMENT;  
  MODEL 'Number_stone_evts_6month'=Treatment Kidney_Stone_Event_Baseline  
/OFFSET=Ln_Number_Of_Months_Exposed DIST=POISSON LINK=LOG DSCALE;  
  EXACT Treatment Kidney_Stone_Event_Baseline / ESTIMATE;  
RUN;
```

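### The Day 90–180 standardisation is extended to every efficacy AUC, so the exploratory Day 1–180 oxalate AUC is divided by the wrong time span (minor)

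*SAP*

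**What the plan says.** SAP 6.1.9, under Area Under the Curve, plots percent change from baseline in 24-hour urinary oxalate (Uox) against time. Area below zero counts as positive and area above zero as negative. On the time axis it says "The AUC will be calculated using the actual time in days between Uox collections, and not the nominal visit days".

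The text after SAP Figure 1 describes the Day 90–180 AUC and then says "The final AUC for each subject will be standardized based on 90 days". The formula is the AUC divided by the actual days from the Day 90 visit to Day 180, times 90. If the Day 90 or Day 180 date is missing, "the standardization will assume the actual number of days elapsed to be 90". No other standardisation is given.

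SAP 8 opens with a general statement: "All AUC parameters referenced in the efficacy analysis refer to the standardized AUCs defined in section 6.1.9". SAP 8.4 then applies the primary model, in the ITT population, to the protocol's exploratory endpoint for 6-month burden (Protocol 3): "AUC of 24-hour Uox from Day 1 to Day 180, based on percent change from Baseline".

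**The concern.** Read together, SAP 6.1.9, 8 and 8.4 instruct the programmer to divide an area of about 179 days by a gap of about 90 days. Two things follow.

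- **Scale.** The result is not a 90-day AUC. It cannot be set beside the primary AUC or read as an average percent reduction.
- **Participant-specific factor.** Each participant's full-period area is multiplied by 90 divided by that participant's own Day 90–180 gap. That gap is not the length over which the area was accumulated. Participants with the same oxalate reduction then receive different values because of visit timing alone. A participant lacking a Day 90 or Day 180 date is handled by a different rule, with 90 days assumed.

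What is at stake is the protocol's only endpoint for oxalate burden over the whole six months. It is tertiary/exploratory and lies outside the testing sequence in SAP 6.1.4.

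**Working it through.** **Inputs**

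- Formula and its scope: SAP 6.1.9 and SAP 8.
- Scale: SAP 3.2 says the AUC "in the active arm is assumed to be 3600 based on a 40% decrease over the 90 days".
- Visit windows: Day 90 ± 3 and Day 180 ± 5 (Protocol 1.3; SAP Table 1).
- Assumptions for illustration: a constant 40% reduction from Day 1, with collections falling on the visit days.

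**1. The plan's own figure.** Day 90–180 at a constant 40%: 40 × 90 = 3600, and (3600 / 90) × 90 = 3600. This reproduces SAP 3.2, so the formula is right for the interval it names.

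**2. Day 1–180 under the same formula.** Raw area = 40 × (last day − 1). SAP value = raw area × 90 / gap. Matching-span value = raw area × 90 / (last day − 1).

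| Day 90 visit, Day 180 visit | Gap (days) | Raw area | SAP value | Matching span, per 90 days |
|---|---|---|---|---|
| 90, 180 | 90 | 40 × 179 = 7160 | 7160 × 90/90 = 7160 | 7160 × 90/179 = 3600 |
| 93, 175 | 82 | 40 × 174 = 6960 | 6960 × 90/82 = 7639 | 6960 × 90/174 = 3600 |
| 87, 185 | 98 | 40 × 184 = 7360 | 7360 × 90/98 = 6759 | 7360 × 90/184 = 3600 |

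At a 90-day gap the formula returns the raw area unchanged, which is 7160/3600 = 1.99 times the value that stands for 40% on the 90-day scale.

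Between the two window extremes, raw areas differ by 7360/6960 = 1.06. After the formula the ratio is 7639/6759 = 1.13, with the order reversed. The matching span removes the difference.

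**3. Missing visit date.** Suppose the second participant lacked only the Day 90 date. The gap is then taken as 90 and the value is 6960 instead of 7639, for the same reduction over the same period.

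**4. Size of the artificial variation.** Assume whole visit days, equally likely across both windows, and the same 40% reduction. The SAP value then has mean about 7168 and SD about 203, or 203/7168 = 2.8%. The assumed effect size of 1.2 on 3600 implies an SD of 3600/1.2 = 3000 for the primary AUC. Against that, the artefact is (203/3000)² = 0.5% of the variance. If the SD doubled with the doubled span (an assumption), it would be (203/6000)² = 0.1%.

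**5. Start of the curve.** The schedule has no 24-hour urine collection on Day 1. Baseline is the mean of two screening collections (SAP 6.1.2), and time runs between actual collections. The SAP does not say what value the curve takes on Day 1.

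**The case against.** The strongest reply is that the formula was plainly meant for Day 90–180. The paragraph that contains it is about that interval, and Protocol 9.1 speaks of standardising to 90 days only for partial data within it. This is probably right about intent, but SAP 8 says otherwise in terms, and no other divisor is supplied.

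Several stronger readings are tempting, and the documents do not support them.

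- **That all efficacy AUCs are wrong.** The primary AUC and the oxalate-to-creatinine AUC cover Day 90–180 and get the matching divisor.
- **That a 40% reduction would be reported as about 80%.** The SAP never converts an AUC to a percentage. The correspondence of 3600 with 40% appears only in the sample-size assumption. The figure of 7160/90 = 79.6% arises only if a reader divides a Day 1–180 value by 90.
- **That the test is distorted by a factor of two.** A factor common to all participants leaves the ANCOVA p-value unchanged.
- **That visit windows give a spread of 6576 to 7859.** This holds the area at 179 days while the gap moves to 98 or 82. Within the windows those gaps occur only when the Day 180 visit itself moves, so the consistent range is 6759 to 7639.
- **That the curve might begin at a screening collection.** The endpoint is defined from Day 1, and change at baseline is 0% by definition. The missing anchor needs stating, but it does not license an earlier start.

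It also stands that the added variation is small and that the endpoint carries no alpha.

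**Conclusion.** The point holds as a minor defect confined to one exploratory endpoint. As written, the SAP divides the Day 1–180 area by the Day 90–180 gap. This gives equal responders unequal values: 6759 to 7639 across the visit windows for a constant 40% reduction, against a single value under the matching divisor. It also leaves the result at about twice the 90-day scale.

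The figures assume a constant reduction and collections on the visit days. The estimate of added variation also assumes visit days equally likely across the windows; allowing for collections up to 7 days before a visit could widen it somewhat. The primary conclusion, the key secondary endpoint and the testing sequence are untouched.

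This is more than missing detail, because a stated rule, followed literally, produces a wrong quantity.

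**What to change.** 1. In SAP 6.1.9 and SAP 8, limit the 90-day formula, its missing-date rule and the general statement to the AUCs that run from Day 90 to Day 180.
2. For the Day 1–180 AUC, anchor the curve at 0% change on Day 1, integrate to the Day 180 collection and divide by the actual days from Day 1 to that collection. Report it per 180 days or as a mean percent reduction. A constant 40% reduction then gives 7200 per 180 days, or 40%, for every participant in the table.

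The cost is a few sentences in the SAP and a small programming change, best made before unblinding. No data collection changes.

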## Quality-of-life Questionnaires

### Adults - SF-36

As part of the Medical Outcomes Study (MOS), a multi-year study to explain variations in participant outcomes, RAND developed the 36-Item Short Form Health Survey (SF-36). The SF-36 is a set of generic, coherent, and easily administered quality-of-life measures that taps 8 health concepts: physical functioning, bodily pain, role limitations due to physical health problems, role limitations due to personal or emotional problems, emotional well-being, social functioning, energy/fatigue, and general health perceptions. It also includes a single item that provides an indication of perceived change in health. The 36 items are identical to the MOS SF-36 described in Ware and Sherbourne. Participants respond to each item on a categorical scale. Categorical answers are transformed to a range of 0 to 100. In addition to the eight health concept scales, two component summary measures are also calculated: PCS (physical component summary), and MCS (mental component summary). All items are scored so that a high score defines a more favorable health state.

For this study, the SF-36 questionnaires will be scored by the algorithm outlined in Appendix 2 based on the manual "How to Score version 2 of the SF-36 Health Survey" (Ware JE, et al. 2000). Additional detail on each of the domain and summary scores are contained therein.

### Adults - EQ-5D-5L

The 5-level EQ-5D version (EQ-5D-5L) was introduced by the EuroQol Group in 2009 to improve the instrument's sensitivity and to reduce ceiling effects, as compared to the previously 3-level EQ-5D. The EQ-5D-5L consists of the EQ-5D descriptive system and the EQ visual analog scale (EQ VAS).

The descriptive system comprises 5 dimensions: mobility, self-care, usual activities, pain/discomfort and anxiety/depression. Each dimension has 5 levels: no problems, slight problems, moderate problems, severe problems and extreme problems. Participants are asked to indicate their health state by ticking the box next to the most appropriate statement in each of the

5 dimensions. This decision results in a 1-digit number that expresses the level selected for that dimension. The digits for the 5 dimensions can be combined into a 5-digit number that describes the participant's health state. It should be noted that the numerals 1 to 5 have no arithmetic properties and should not be used as a cardinal score.

The values collected for the 5 health dimensions will be used to calculate an EQ-5D-5L index value. Index values will be calculated based on the US value set. Additional details are contained in a separate users guide document.

The EQ VAS records the participant's self-rated health on a 20-cm vertical VAS, where the endpoints are labelled 'The best health you can imagine' and 'The worst health you can imagine'. Participants are asked to place an "X" on the line that represents their health on that day. The VAS can be used as a quantitative measure of health outcome that reflect the participant's judgement.

### **Pediatrics - PedsQL**

The PedsQL™ is a modular approach to measuring health related quality of life (HRQOL) in healthy children and adolescents and in those with acute and chronic health conditions. The multidimensional PedsQL Generic Core Scales were designed to measure the 3 core dimensions of health as delineated by the World Health Organization (WHO) in 1948 (physical, emotional, and social functioning), as well as role (school) functioning.

Questionnaires are administered to the participant and the participant's parent. The 23-item PedsQL™ is comprised of 5 items in the Emotional, Social and School Functioning dimensions (Psychosocial Health) and 8 items in the Physical Functioning (Physical Health) dimension. The questionnaire has specific versions for the child and the child's parent based on the age of the participant (5-7 years old, 8-12 years old, 13-18 years old). Questionnaires are administered based on the age of participant at baseline. The same version of the questionnaire will be used throughout the course of the study for a given participant based on age at baseline. Additionally, the family impact module is administered to the participant's parent.

Items are reverse-scored on a 0 to 4 Likert scale and linearly transformed to a 0 to 100 scale. Scale scores are computed as the sum of the items divided by the number of items answered (this accounts for missing data). If more than 50% of the items in the scale are missing, the scale score is not computed. Higher scores indicate better functioning and HRQOL. Further details and scoring instructions are provided in a separate document.

